⁹⁹Tc-MDP in Postmenopausal Women With Differentiated Thyroid Cancer and
Osteoporosis

Trial registration: NCT02304757

April 16, 2021

Study Protocol

Study Type: Interventional

Study Design: Treatment, Parallel Assignment, Single Blind (Outcomes Assessor), Non-Randomized, Efficacy Study

Patients recruitment

This was an open-label, prospective non-randomized study carried out in three centers (ClinicalTrials.gov ID: NCT02304757) from November 2015 to December 2019. Postmenopausal women are eligible in the study fulfilling all the following criteria. (1) They were pathologically diagnosed with DTC including papillary or follicular carcinoma. (2) They received a near total thyroidectomy and radioiodine treatment. (3) TSH suppression should be at least one year before the study. (4) Bone mineral density (BMD) in lumbar spine and/or hip was tested by Dual-energy X-ray absorptiometry (DXA) at baseline, 6 month (m) and/or 12m follow up. 5) The diagnosis of osteoporosis was T-score ≤ -2.5 SD at the lumbar spine, or hip.

We excluded patients considering the following criteria: (1) patients having medications for OS before TSH suppression treatment; (2) secondary OS; (3) severe liver or kidney disease; (4) myelosuppression; (5) digestive disease; (6) long term use of immunosuppressive agent, estrogen or estrogen receptor modulators. This study was approved by the Institutional Review Board of Hospital Research Ethics. All the patients were fully acquainted with their treatment and consented to participate in the clinical trial.

TSH suppression treatment

TSH suppression treatment was based on the risk stratification of DTC using levothyroxine (L-T₄) as recommended

Treatment protocol for osteopenia and osteoporosis

Patients with OS were divided into ⁹⁹Tc-MDP and alendronate treatment groups.

1. ⁹⁹Tc-MDP treatment group: 15mg ⁹⁹Tc-MDP were intravenously administered twice a week for 10 weeks, then once a week for 8 weeks, every two weeks for 22

weeks and monthly for another 3m.

2. Alendronate treatment group: 70mg alendronate (Merck & Co., Darmstadt, Germany) was administered orally once a week for 12m.

Laboratory assays

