Bone alkaline phosphatase (ALP), osteocalcin and propeptide of type I procollagen (PINP), and C-terminal telopeptide of type I collagen (CTX) were all determined by enzyme-linked immunosorbent assay (Modular E170, Hoffmann-La Roche, Basel, Switzerland). Free T₃, free T₄, thyroid stimulating hormone (TSH) was measured using a time-resolved immunofluorometric assay (Anytest, sym-bio lifescience co., ltd, Shanghai, China). 25(OH) D, parathyroid hormone (PTH), serum calcium and phosphorus and other laboratory tests were measured as routine at baseline and 12m.

Analysis of knee relief, QOL and adverse reaction

Lysholm knee (LYS) rating scale was used to evaluate the knee function at baseline and 12m. QOL in patients with OS was measured with a 36-item Short Form Health Status Survey questionnaire (SF-36) at baseline and 12m. SF-36 including four physical and fundamental items were calculated which represent the deviation from the reference population. The higher score by SF-36 and LYS means a better QOL and knee function. A treating physician reviewed the clinical results and any discomfort at each visit.

Statistical Analysis Plan

The predetermined primary end point was the difference in the change in BMD of the lumbar spine between the two groups. Sixty four sample size was assumed to achieve 80% power to detect non-inferiority using a one-sided two sample t-test. The margin of non-inferiority is 0.5% percent. The true difference between the means is assumed to be 0. The significance level (alpha) of the one sided test is 0.025. The data were drawn from population with standard deviations of 0. Consider the 10% loss of

follow-up rate, group sample size was 70 cases.

Continuous data are expressed as the mean \pm standard deviation. Independent sample t-test by SPSS 22 was used to compare the basic information, clinical characteristics within groups at baseline and the difference values of BMD between that at baseline and 6m and 12m after treatment. Differences in BMD, QOL by SF-36 questionnaire, bone turnover marks and other laboratory results were determined using a paired t-test (one-sided tests) and Mann-Whitney U test. A Fisher exact test was used to compare the adverse events. Pearsman Rho was used to analyze the correlation of lumbar uptake of Na^{18}F and BMD/T value by DXA. P value <0.05 was considered statistically significant.

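### Adverse-event review is tied to undefined visits; if infusion attendances count as visits, the unadjusted Fisher comparison is open to ascertainment bias

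*Combined protocol and SAP*

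**What the plan says.** The section on knee relief, QOL and adverse reaction (combined protocol and SAP) closes with the only description of how adverse events are gathered: "A treating physician reviewed the clinical results and any discomfort at each visit". No section says what counts as a visit, how many there are in either group, or which questions are asked.

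The treatment protocol section gives very different dosing contacts. ⁹⁹Tc-MDP doses "were intravenously administered twice a week for 10 weeks, then once a week for 8 weeks", followed by "every two weeks for 22" "weeks and monthly for another 3m". Alendronate "was administered orally once a week for 12m", and no attendance for dosing is stated.

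The assessments scheduled without reference to treatment group are few. DXA is at baseline and at 6m and/or 12m (Patients recruitment). Lysholm, SF-36 and routine laboratory tests are at baseline and 12m.

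The Statistical Analysis Plan covers the comparison in one sentence: "A Fisher exact test was used to compare the adverse events". The general threshold is P<0.05. Nothing adjusts for number of contacts. The study is described as open-label and non-randomized, with a blinded outcomes assessor.

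**The concern.** A Fisher test on the proportions of women with an event compares true risks only if an event is equally likely to be recorded in both groups. Nothing in the plan secures that, and the dosing schedules work against it. A woman who attends for frequent infusions has many occasions to mention a passing complaint. A woman taking a weekly tablet at home may be asked twice in a year, when a mild or resolved symptom may be forgotten.

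The likely direction is clear. Extra opportunities to record would raise the ⁹⁹Tc-MDP count relative to alendronate. That could produce a significant difference where the true risks are equal, or conceal a real excess on alendronate. The person recording is the treating physician in an open-label study, so knowledge of treatment could add to any imbalance.

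**Working it through.** **Step 1: contacts implied by the schedule** (inputs from the treatment protocol section).
- Twice weekly for 10 weeks: 2 × 10 = 20
- Weekly for 8 weeks: 8
- Every two weeks for 22 weeks: 22 / 2 = 11
- Monthly for 3 months: 3
- Total: 20 + 8 + 11 + 3 = 42, or 44 if both end points of the last two phases are counted (20 + 8 + 12 + 4)

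For alendronate, the stated time points are baseline plus 6m and/or 12m, so 2 to 3.

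**Step 2: what this could do to the Fisher test.** The plan states no figure to reproduce. The group size of 70 comes from the Statistical Analysis Plan and is read as per group. True risks and capture probabilities are assumptions.

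Recorded rate = true risk × capture probability. The chance of two-sided Fisher P<0.05 is the sum, over all pairs of counts from 0 to 70 in each group that reach P<0.05, of the product of the two binomial probabilities. This is exact enumeration, not simulation.

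| True risk, both groups | Capture, ⁹⁹Tc-MDP v alendronate | Recorded rates | Chance of P<0.05 |
|---|---|---|---|
| 20% | 90% v 90% | 18% v 18% | 3.1% |
| 20% | 90% v 70% | 18% v 14% | 6.6% |
| 20% | 90% v 50% | 18% v 10% | 21% |
| 30% | 90% v 90% | 27% v 27% | 3.1% |
| 30% | 90% v 70% | 27% v 21% | 9.3% |
| 30% | 90% v 50% | 27% v 15% | 34% |
| 40% | 90% v 90% | 36% v 36% | 3.3% |
| 40% | 90% v 70% | 36% v 28% | 13% |
| 40% | 90% v 50% | 36% v 20% | 49% |

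At 90% v 50%, virtually all of these false positives point against ⁹⁹Tc-MDP.

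**Step 3: masking.** Suppose the true risks are 20% on ⁹⁹Tc-MDP and 40% on alendronate. With 90% capture in both groups the recorded rates are 18% v 36%, and the chance of P<0.05 is 61%. With capture of 90% v 50% the recorded rates are 18% v 20%, and the chance falls to 4%.

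**The case against.** The strongest reply is that unequal review is inferred, not stated. The plan does not say that an infusion attendance is a visit at which discomfort was reviewed, nor how often women on alendronate were seen or contacted. The sentence couples discomfort with clinical results and ends a section whose dated assessments are at baseline and 12m. It can be read as meaning assessment visits common to both groups, and on that reading the mechanism disappears. This stands. A reader might infer that the comparison is biased by design; the documents support only that it is open to bias.

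The size is also assumed. Nothing links 42 infusions to 90% capture, or two assessments to 50%. The result runs from small to large depending on those inputs. This stands too.

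Two further inferences go beyond the text. One is that safety is a main ground for choosing between the drugs. The plan calls the study an efficacy study, its primary end point is lumbar spine BMD, and it states no safety objective. The other is that review by the treating physician contradicts the blinded-assessor label. No section says that the label extends to adverse events, so no conflict is shown, only missing detail.

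Finally, a test confined to shared assessments could drop transient infusion-related events and understate harm in the intravenous group. That is right, and it is why such a test should supplement the all-events comparison and not replace it.

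None of this removes the gap. As written, the plan does not let a reader tell whether the two groups were asked equally often.

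**Conclusion.** The point holds conditionally. Adverse-event review is tied to visits that the plan leaves undefined. One group has 42 scheduled infusion attendances and the other has no stated attendance beyond 2 to 3 assessments, and the Fisher test takes no account of this. If infusion attendances count as review visits and women on alendronate were seen less often, the comparison is open to ascertainment bias, most likely against ⁹⁹Tc-MDP.

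The documents cannot give the size. Under the assumptions shown, the chance of a spurious significant result is about 7% to 13% with a modest capture gap (90% v 70%) and 21% to 49% with a wide one (90% v 50%), against about 3% with equal capture. Those figures rest on assumed true risks of 20% to 40%, assumed capture rates, and 70 women per group. If review took place only at common visits, this mechanism does not apply.

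**What to change.** - Define what counts as a visit for adverse-event review, and report the number of contacts per group.
- Put the same short discomfort checklist to both groups at the shared assessments: 12m for all, and 6m where attended. Run a Fisher test on that common record as the like-for-like between-group comparison.
- Report all recorded events beside it, identifying separately those found only at infusion visits.

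The documents give recruitment and conduct as November 2015 to December 2019, so a new checklist may no longer be possible. If data collection is finished, restrict the like-for-like comparison to events recorded at the shared time points, as far as the records allow, and keep the all-events report.

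The cost is a short checklist at assessments that already exist, or a re-tabulation of existing records, plus a few sentences in the SAP. The drawback is that the common-record test may miss transient events, so it must not stand alone.

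### The non-inferiority margin is in percent, but the BMD endpoint and its t-test are not defined on a percent scale and nothing is compared with the margin

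*Combined protocol and SAP*

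**What the plan says.** All the relevant text is in the Statistical Analysis Plan section of the combined protocol and SAP.

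- **Endpoint:** "The predetermined primary end point was the difference in the change in BMD of the lumbar spine between the two groups". No unit, scale or timepoint is attached.
- **Margin:** "The margin of non-inferiority is 0.5% percent".
- **Sample size:** "Sixty four sample size was assumed to achieve 80% power to detect non-inferiority using a one-sided two sample t-test", with a true difference of 0 and 10% loss to follow-up, giving 70 cases as the group size. "The significance level (alpha) of the one sided test is 0.025".
- **Analysis:** an independent-sample t-test in SPSS is applied to baseline characteristics and to "the difference values of BMD between that at baseline and 6m and 12m after treatment". The next sentence adds a one-sided paired t-test and a Mann-Whitney U test for BMD differences and other outcomes.
- **Decision rule:** "P value <0.05 was considered statistically significant". The margin is not mentioned again after the sample-size paragraph.

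**The concern.** A non-inferiority conclusion rests on one comparison: a confidence bound, or a test shifted by the margin, set against a threshold in the same unit. Here the threshold carries a percent sign. The endpoint and the analysis variable are worded as change and difference values, which would ordinarily be a follow-up value minus a baseline value in BMD units. The plan neither defines percent change nor says what the margin is a percentage of.

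The analysis paragraph also never uses the margin. An ordinary independent t-test addresses a null difference of zero. A P value below 0.05 from it does not show non-inferiority, and neither does one above 0.05.

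At stake is whether the trial's conclusion was fixed in advance. The groups are not randomised (Study Design), so their baseline BMD may differ. Absolute and percent change can then give different between-group differences. If the scale is left open, it is chosen by whoever analyses the data.

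**Working it through.** **1. Does the sample size show which scale was meant?**

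Inputs from the Statistical Analysis Plan: margin 0.5, true difference 0, one-sided alpha 0.025, power 80%. The SD is printed as 0, without a unit. A digit may have been lost when the text was read from PDF, so nothing here rests on that figure.

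Normal approximation per group: n = 2 x (SD/margin)^2 x (1.960 + 0.842)^2.

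- With the printed SD of 0, n = 0, so 64 does not follow from the inputs as printed.
- With SD = 1.0, n = 2 x 4 x 7.85 = 62.8, rounded up to 63. The exact t calculation gives 64, with power 80.1%.
- Dropout: 64 x 1.1 = 70.4, or 63/0.9 = 70.0, so 70 per group is consistent. (64/0.9 = 71.1, which rounds up to 72.)

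So 64 per group corresponds to an SD of about 1.0 in the margin's own unit. Only the ratio SD/margin, about 2.0, enters the formula. The calculation is the same for percent change and for absolute change with the margin converted, so it does not settle the scale.

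**2. Setting the statements side by side**

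| Element | Wording in the plan | Scale stated? |
|---|---|---|
| Primary endpoint | change in lumbar spine BMD | no |
| Margin | 0.5, in percent | percent, but of what is not said |
| Planning SD | printed as 0 | no unit |
| Between-group t-test | difference values of BMD, 6m and 12m | no |
| Decision rule | P < 0.05 | no link to the margin |

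Only the margin carries a unit, and no sentence links it to the test.

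**3. How much could the scale matter? (assumed values only)**

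The documents give no baseline BMD, imbalance or expected gain.

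- Margin in BMD units: 0.005 x 0.6 = 0.0030 and 0.005 x 0.9 = 0.0045 g/cm2.
- Equal 4% gains, mean baseline 0.725 g/cm2, margin 0.005 x 0.725 = 0.003625 g/cm2:
  - imbalance 0.01: 0.04 x 0.01 = 0.0004; 0.0004/0.003625 = 11% of the margin;
  - imbalance 0.05 (0.70 against 0.75): 0.04 x 0.05 = 0.002; 0.002/0.003625 = 55% of the margin.
- Equal absolute gains of 0.028 g/cm2 instead:
  - baselines 0.72 and 0.73: 3.89% against 3.84%, a gap of 0.053 points before rounding; 0.053/0.5 = 11% of the margin;
  - baselines 0.70 and 0.75: 4.00% against 3.73%, a gap of 0.27 points; 0.267/0.5 = 53% of the margin.

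The distortion runs either way, depending on which kind of gain is equal.

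**The case against.** The strongest reply is that the plan is loosely worded rather than inconsistent. The margin is the only scale indication given, and it is in percent. If the authors wrote of difference values but meant percent change, a margin of 0.5 percentage points applies directly. The plan also does not identify the t-test on difference values as the non-inferiority test; that test is named only in the sample-size paragraph. Both observations stand. A reader might infer that the plan prescribes an analysis of raw BMD in g/cm2, so that the margin cannot be applied at all. The documents do not support that: they never use the words raw, absolute or g/cm2.

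Two other readings should also be set aside. Taking 0.5 as g/cm2 ignores the printed percent sign, and the implied SD of about 1.0 would exceed the whole assumed BMD of 0.6 to 0.9 g/cm2. Reading the doubled unit as 0.005 percentage points strains what looks like a simple repetition.

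It is also fair to say that the 11% to 55% range comes from assumed cases, and that equal absolute gains produce a similar shift on the percent scale. The illustration therefore does not show that percent change is the better scale, nor that percent change removes baseline imbalance. The case for percent is that it matches the printed margin.

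The loose-wording reply leaves two gaps. Percent change is defined nowhere, and even if it was meant, the analysis paragraph still compares nothing with the margin and uses a P threshold that differs from the planning alpha.

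**Conclusion.** The concern holds as a failure to define the scale and the decision rule. It is not a proven clash of units. Endpoint, margin, SD and test are not shown to share a scale, and the analysis section contains no step that turns the t-test into a non-inferiority decision. Followed literally, the plan cannot deliver its primary conclusion without an assumption supplied by the analyst.

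The effect in this trial cannot be quantified from the documents. On the assumed values, the choice of scale alone could use roughly a tenth to a half of the margin. That could change a close result but need not change a clear one. The sponsor should correct this, since the margin decides the trial's claim.

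**What to change.** - Define the primary variable as percent change in lumbar spine BMD, 100 x (follow-up - baseline)/baseline, at one named timepoint, for example 12m, the end of treatment.
- State the margin as -0.5 percentage points for 99Tc-MDP minus alendronate.
- Claim non-inferiority only if the lower limit of the two-sided 95% confidence interval is above -0.5. This corresponds to one-sided alpha 0.025; state that the general P < 0.05 rule does not govern this comparison.
- State the planning SD on the same scale. With 64 per group and 80% power it is about 1.0 percentage point, and its source should be given.
- Report absolute change as a sensitivity analysis.

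Naming 12m requires a rule for women scanned only at 6m, because the eligibility criteria under Patients recruitment allow follow-up DXA at 6 and/or 12 months.

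The cost is SAP wording and re-analysis of BMD values already collected. The drawback is timing: the study period ended in December 2019 and the document is dated April 2021. The choice of scale and timepoint should therefore be labelled as a clarification, not presented as pre-specified, and results should be shown on both scales so that readers can see whether the conclusion depends on it.

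### The trial is sized for non-inferiority, but the analysis text as written tests lumbar spine BMD change against zero difference, not against the 0.5% margin

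*Combined protocol and SAP*

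**What the plan says.** Everything on this point is in the Statistical Analysis Plan section, in two adjacent paragraphs.

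The first paragraph sets the objective:

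- Endpoint: "The predetermined primary end point was the difference in the change in BMD of the lumbar spine between the two groups".
- Sizing: 64, for 80% power "to detect non-inferiority using a one-sided two sample t-test".
- Margin: "The margin of non-inferiority is 0.5% percent".
- Assumed effect: "The true difference between the means is assumed to be 0".
- Alpha: "The significance level (alpha) of the one sided test is 0.025".
- Spread: "The data were drawn from population with standard deviations of 0".
- After allowing for 10% loss: "group sample size was 70 cases".

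The second paragraph says how the data are analysed. An independent-sample "t-test by SPSS 22 was used to compare the basic information, clinical characteristics within groups at baseline and the difference values of BMD", at 6 and 12 months. A further sentence applies a paired t-test, marked one-sided, and the Mann-Whitney U test to BMD, quality of life and laboratory results. A single threshold of P<0.05 closes the paragraph. Nothing in it refers back to non-inferiority, the margin or 0.025.

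**The concern.** One sentence assigns the same unqualified t-test to baseline characteristics and to BMD change. For baseline characteristics the null can only be zero difference, and nothing says the BMD comparison is different. A test of zero difference and a test against a margin ask different questions.

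The plan assumes the true difference is 0, so the expected result of the written test is non-significance. That does not show non-inferiority, because it may simply reflect an imprecise estimate. The plan does not tell the reader to treat non-significance as non-inferiority, but its analysis text gives no other way to reach the conclusion the trial was designed for. At stake is the success criterion of the only primary endpoint.

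A smaller point concerns alpha. The sidedness of P<0.05 is not stated for the independent t-test. If it is two-sided, each tail is 0.025, which agrees with the sizing. If it is one-sided, a margin test would run at 5%, not 2.5%. This is an ambiguity, not a proven conflict.

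**Working it through.** **Inputs.** From the plan: margin 0.5, true difference 0, one-sided alpha 0.025, power 80%, n = 64. Assumptions: 64 is per group (because 70 is called a group size), allocation is 1:1, SDs are equal, and the SD is on the same scale as the margin. The printed SD of 0 is unusable, so a range is shown.

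**Reproducing the plan's n.** n per group = 2 × SD² × (1.960 + 0.842)² / 0.5².

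- SD 0 gives n = 0, so 64 does not follow from the printed inputs.
- SD 1.0 gives 2 × 7.85 / 0.25 = 62.8, rounded up to 63. With the non-central t distribution, 64 per group has 80.15% power.

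SD 1.0 is therefore the value most consistent with the plan's own n.

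**Comparing the two rules.** With n = 64 per group, df = 126, t(0.975) = 1.979 and SE = SD × √(2/64). Let d be the observed difference, 99Tc-MDP minus alendronate.

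- Zero-difference test, two-sided 0.05: non-significant when |d| < 1.979 × SE.
- Margin test, one-sided 0.025: passes when d > -0.5 + 1.979 × SE.

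| SD | SE | Non-significant within | Margin test passes above | Non-significant but non-inferiority not shown |
|---|---|---|---|---|
| 0.7 | 0.124 | ±0.245 | -0.255 | none |
| 1.0 | 0.177 | ±0.350 | -0.150 | -0.35 to -0.15 |
| 1.5 | 0.265 | ±0.525 | +0.025 | -0.52 to +0.02 |
| 2.0 | 0.354 | ±0.700 | +0.200 | -0.70 to +0.20 |

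**Example, SD 1.0 and d = -0.30.**

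- 95% CI: -0.30 ± 0.35, or -0.65 to +0.05.
- Zero-difference test: t = -0.30/0.177 = -1.70, two-sided P = 0.09.
- Margin test: t = (-0.30 + 0.50)/0.177 = 1.13, one-sided P = 0.13.

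The written test finds no difference, and non-inferiority is not shown.

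**Conditional illustration: non-significance read as non-inferiority.** The plan does not say to do this. The chance that a true deficit of 0.5 would pass, by non-central t, against a planned 2.5%:

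| n per group | SD 0.7 | SD 1.0 | SD 1.5 | SD 2.0 |
|---|---|---|---|---|
| 64 | 2.0% | 19.9% | 53.5% | 71.1% |
| 70 | 1.3% | 16.4% | 50.1% | 68.8% |
| 32 (if 64 were the total) | 19.7% | 49.6% | 74.1% | 83.4% |

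At 64 per group there is no inflation over 2.5% below SD 0.72.

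**Conditional illustration: P<0.05 one-sided, applied to the margin.** Type I error is 5%. At SD 1.0 and 64 per group, the pass mark moves from -0.150 to -0.5 + 1.657 × 0.177 = -0.207.

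**The case against.** The best defence is that the sizing text stands under the same heading, directly after the primary endpoint. It names a non-inferiority hypothesis, a one-sided two-sample t-test, a margin and an alpha. The t-test in the next paragraph is the same kind of test, and no null is stated for it. A sympathetic reader could therefore infer the intended analysis. That is fair as to intent. But those sentences are worded as power assumptions, and the analysis paragraph carries none of them forward. It groups the BMD comparison with the baseline variables, uses another threshold and covers two time points. Someone executing it would not run the sized test.

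Other points against:

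- The alpha contrast is not an error in itself. This stands, and alpha is treated here only as an ambiguity.
- The error rates of 20% to 71% depend on a reading the plan does not instruct. This stands. The 20% is also simply 1 minus the 80% power. At SD 1.5 and 2.0, power against the margin would be only 46% and 29%, so those rows apply only if the plan's power claim is wrong. At SD 1.0 with a true difference of 0, the trial would land in the disagreement band about 17% of the time.
- The Mann-Whitney test, which is also between groups, is listed for BMD. This stands as a further reason to name one primary test. The paired t-test is within-group and does not compete with it.
- An unadjusted interval in a non-randomized study does not remove confounding. True, but that is a separate matter from which null is tested.

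**Conclusion.** The concern holds, and the plan is wrong as written. The primary endpoint is sized for non-inferiority, but the only instruction for analysing it tests zero difference and contains no rule that yields a non-inferiority conclusion. This follows from the text and needs no SD.

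The practical size does depend on the SD, which the plan does not usably give. At SD 1.0 the two rules disagree over a band 0.20 wide, at 2.0 over a band 0.90 wide, and at 0.7 hardly at all. These figures assume 64 per group, equal SDs and a margin on the same scale as the SD. Because it concerns the sole primary endpoint, the point must be fixed.

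**What to change.** Replace the BMD part of the t-test sentence with wording such as:

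> The primary analysis estimates the between-group difference (99Tc-MDP minus alendronate) in lumbar spine BMD change, on the scale of the 0.5% margin, with a two-sided 95% CI. Non-inferiority is concluded only if the lower limit lies above -0.5%, which is equivalent to the one-sided 0.025 test used for sizing. The P<0.05 rule and the paired and Mann-Whitney tests of BMD apply to secondary comparisons only.

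The sponsor must confirm two things the plan leaves open: the scale of the margin, since the printed unit is ambiguous, and whether 6 or 12 months is the primary time point.

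The cost is SAP wording and one confidence interval, with no new data and no change to the margin or sizing alpha. The document is dated April 2021, after the stated study period of November 2015 to December 2019. New wording cannot restore prespecification, and a rule added after the data were seen should be labelled post hoc. The result may also be less favourable: at SD 1.0 and 64 per group the observed difference must exceed -0.15, against -0.21 for a margin test at one-sided 0.05.

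### The paired t-tests are one-sided at P<0.05 with no direction stated, a looser one-sided level than the 0.025 set for the primary test

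*Combined protocol and SAP*

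**What the plan says.** Four statements in the Statistical Analysis Plan bear on this point.

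- The analysis-methods sentence opens with "Differences in BMD, QOL by SF-36 questionnaire" and ends "bone turnover marks and other laboratory results were determined using a paired t-test (one-sided tests) and Mann-Whitney U test". It therefore covers BMD, SF-36, bone markers and other laboratory results. The one-sided label is attached to the paired t-test.
- The section closes with one general threshold: "P value <0.05 was considered statistically significant". No separate level is given for one-sided tests.
- For sample size, "The significance level (alpha) of the one sided test is 0.025". This refers to the two-sample non-inferiority comparison.
- The primary endpoint is a between-group comparison: "The predetermined primary end point was the difference in the change in BMD of the lumbar spine between the two groups". BMD changes are also given an independent-sample t-test on "the difference values of BMD between that at baseline and 6m and 12m after treatment".

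The closest the document comes to a direction is in the section on knee relief, QOL and adverse reaction: "The higher score by SF-36 and LYS means a better QOL and knee function". The Laboratory assays section lists bone markers, thyroid hormones and further tests ("25(OH) D, parathyroid hormone (PTH), serum calcium and phosphorus and other laboratory tests were measured as routine at baseline and 12m") without saying which way any of them is expected to move.

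**The concern.** A one-sided test is not fully specified until its direction is given, because the same data yield two different P values depending on the tail. The SF-36 sentence says how the scale runs, which is not an alternative hypothesis, and the bone markers and laboratory values have not even that.

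Two things are at stake. First, for measures such as calcium, PTH or TSH a shift either way would be of interest, and a one-sided test cannot declare one of the two. Second, in the tested direction the supporting results meet a looser standard than the primary result: one-sided 0.05 against one-sided 0.025. A reader who sees P<0.05 throughout the report would not know that the paired results were judged on a different scale.

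**Working it through.** **Inputs.** The one-sided paired test, the P<0.05 threshold and the primary one-sided 0.025 come from the Statistical Analysis Plan. The plan gives no figure of its own for the paired tests beyond P<0.05, so there is none to reproduce. The number of pairs is an assumption. A group size of 70 less 10% loss gives 70 × 0.9 = 63 pairs per group. If the stated 64 is instead the total for both groups, there are 64/2 = 32. The plan gives no SDs for changes in these measures, so effects are in units of the SD of the within-patient change, and the 0.3 SD shift is illustrative.

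**Step 1: levels.** One-sided 0.05 has critical z = 1.645, the same as a two-sided test at 0.10. One-sided 0.025 has critical z = 1.960, the same as two-sided 0.05. The ratio of the one-sided levels is 0.05/0.025 = 2.

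**Step 2: type I error.** In 200,000 simulated null samples of 64 pairs, the rejection rates were:

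- direction fixed in advance, one-sided 0.05: 0.050
- tail chosen after seeing the data: 0.100
- two-sided 0.05: 0.050

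**Step 3: smallest significant mean change.** This is the critical t divided by √n, with n − 1 degrees of freedom.

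| Pairs | One-sided 0.05 | Two-sided 0.05 |
|---|---|---|
| 63 | 1.670/√63 = 0.210 SD | 1.999/√63 = 0.252 SD |
| 32 | 1.696/√32 = 0.300 SD | 2.040/√32 = 0.361 SD |

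**Step 4: power for a true 0.3 SD shift.** Noncentral t with noncentrality 0.3√n, which is 2.38 for 63 pairs and 1.70 for 32.

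| Pairs | One-sided, shift in tested direction | Two-sided | One-sided, shift in untested direction |
|---|---|---|---|
| 63 | 76% | 65% | 0.003% |
| 32 | 51% | 38% | 0.05% |

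**Step 5: two single results, 62 degrees of freedom.** At t = 1.8, one-sided P = 0.038 and two-sided P = 0.077, so the call of significance flips. At t = −3 with the upper tail tested, one-sided P = 0.998 and two-sided P = 0.0039, so a clear shift goes undeclared.

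**The case against.** A one-sided test in a direction fixed beforehand is legitimate. Its type I error is the same 0.05 as a two-sided test at 0.05, and it gains power where an effect is expected: 76% against 65% with 63 pairs, 51% against 38% with 32. These are also secondary tests. The groups are not matched, so the paired tests are most naturally read as within-group comparisons, although the plan does not say so. In a non-randomized study such comparisons do not establish a treatment difference whichever sidedness is used.

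All of this stands, and it limits the weight of the point. It does not supply the missing direction, explain why the primary test is held to half the one-sided level, or let a one-sided test detect a shift in the other tail.

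Two stronger readings are tempting. A reader might infer that the plan doubles the false-positive rate to 0.10. That holds only if the tail was picked after the data were seen. The document does not say this happened. It also does not rule it out, since it names no direction and is dated after the study period. A reader might also infer that the primary conclusion is compromised. It is not: the primary comparison is a separate two-sample test with its own stated level of 0.025.

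**Conclusion.** The point holds as a gap in the specification and an inconsistency of standard in the secondary analyses. It should be corrected but does not threaten the primary result. Followed as written, the plan calls a paired result significant when one-sided P lies between 0.025 and 0.05, and it cannot declare a change in the untested direction.

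The missing direction, the 0.05 threshold and its contrast with 0.025 rest on the text alone. The sizes rest on assumptions: 63 or 32 complete pairs, normally distributed changes and an illustrative 0.3 SD shift. On these, going one-sided lowers the bar for significance by about 0.04 SD (0.252 − 0.210) with 63 pairs, or 0.06 SD (0.361 − 0.300) with 32. It leaves under 0.1% power against an opposite shift that a two-sided test would declare 65% or 38% of the time. The documents do not support a claim that the error rate actually reached 0.10. Nor do they support extending the one-sided label to the Mann-Whitney U test.

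**What to change.** Keep one-sided 0.025 for the primary non-inferiority test only. State that the paired t-tests on BMD, SF-36, bone turnover markers and laboratory results are two-sided at 0.05, and report each mean change with its 95% confidence interval. Adding directions now while keeping the tests one-sided would be a weaker repair, because the document could not show that they were chosen before the data were seen.

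The document is dated April 2021 and the study ran from November 2015 to December 2019, so the change must be disclosed as post hoc.

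The cost is a short edit to the analysis-methods text and a rerun of the paired tests on data already collected, with no change to the sample size. Power in the expected direction falls (76% to 65%, or 51% to 38%, in the illustration), and results with one-sided P between 0.025 and 0.05 are no longer called significant.
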